8.5 Temporary halt and (prematurely) end of study report.....	26
8.6 Public disclosure and publication policy.....	27
9. REFERENCES.....	28

LIST OF ABBREVIATIONS AND RELEVANT DEFINITIONS

ABR	General Assessment and Registration form (ABR form), the application form that is required for submission to the accredited Ethics Committee; in Dutch: Algemeen Beoordelings- en Registratieformulier (ABR-formulier)
AE	Adverse Event
AR	Adverse Reaction
CA	Competent Authority
CCMO	Central Committee on Research Involving Human Subjects; in Dutch: Centrale Commissie Mensgebonden Onderzoek
CV	Curriculum Vitae
DSMB	Data Safety Monitoring Board
EU	European Union
EudraCT	European drug regulatory affairs Clinical Trials
GCP	Good Clinical Practice
GDPR	General Data Protection Regulation; in Dutch: Algemene Verordening Gegevensbescherming (AVG)
IB	Investigator's Brochure
IC	Informed Consent
IMP	Investigational Medicinal Product
IMPD	Investigational Medicinal Product Dossier
METC	Medical research ethics committee (MREC); in Dutch: medisch-ethische toetsingscommissie (METC)
(S)AE	(Serious) Adverse Event
SPC	Summary of Product Characteristics; in Dutch: officiële productinformatie IB1-tekst
Sponsor	The sponsor is the party that commissions the organisation or performance of the research, for example a pharmaceutical company, academic hospital, scientific organisation or investigator. A party that provides funding for a study but does not commission it is not regarded as the sponsor, but referred to as a subsidising party.
SUSAR	Suspected Unexpected Serious Adverse Reaction
UAVG	Dutch Act on Implementation of the General Data Protection Regulation; in Dutch: Uitvoeringswet AVG
WMO	Medical Research Involving Human Subjects Act; in Dutch: Wet Medisch-wetenschappelijk Onderzoek met Mensen

SUMMARY

Rationale:

People with complex problems on multiple life domains, so called 'hotspotters', receive fragmented care. This is difficult to manage by patients and care providers, leading to little effect of care and persistent unmet needs. The accumulation and complexity of problems often leads to high medical expenses. Next to their high medical spending levels, hotspotters' experiences with the healthcare system are low as the healthcare system is not (yet) successful in dealing with their needs. Interventions aimed at the complex situation of hotspotters in our current healthcare system might benefit by applying a Triple Aim approach. This approach aims to simultaneously improve the individual experience of care, reduce the cost of care per capita and improve the health of populations by offering proactive integrated care.

Objective:

Is proactive integrated care cost-effective and does it result in better patients experience than usual care after 12 months for patients with problems on multiple life domains?

Main and secondary study parameters:

This study will focus on measuring the changes in the following:

1. Incremental cost-effectiveness from a societal perspective. Information on cost will be based on patient-reported data obtained by questionnaires supplied with data from the GP medical files (*Huisarts informatie system, HIS*) and *CBSmicrodata*. To assess the effectiveness the EQ-5D-5L will be used for determining quality of life.

The secondary study parameters are:

1. Insight into patients experience of care, quality of life, proactive coping, and self-efficacy. This information will be gathered using interviews, focus groups and questionnaires (SF-12, UPCC, PAM-13 & Self-efficacy and Intentie itemlist).
2. Process evaluation with the involved care professionals, including the integration level of care per GP-practice, the nature of the communication between healthcare provider and patient (HCCQ, OPTION5), and acceptability (AIM), appropriateness (IAM), feasibility (FIM), and perceived and experienced effectiveness of the intervention.

Study design:

A stepped-wedge cluster randomised controlled trial (RCT) design will be used. This study will be performed in 20 general practices that do not yet offer proactive integrated care for hotspotters. Data on cost-effectiveness will be quantitatively assessed. Patient experience will be qualitatively assessed through focus groups and quantitative using validated questionnaires. Besides, the process will be both qualitatively and quantitatively evaluated using interviews or focusgroups, observations (audio recording) with care professionals on common themes of process evaluation and a validated questionnaire.

Study population:

In total 200 hotspotters will be included. Hotspotters are individuals with at least two incidents of acute care utilisation (defined as out-of-office GP consultations, acute psychiatric care, emergency department visits and unplanned admissions) during the past year, and problems on two out of three health domains (chronic somatic, mental and/or social problems) based on diagnosis (coded with the International Classification of Primary Care) or medication

(ATC) coding.

Intervention:

The proactive integrated care intervention that will be used consists of five steps:

1. Active invitation of the patient from the practice.
2. Consult of 45 minutes with a trained Practice Nurse Mental Health Care based on the Positive Health Methodology.
3. Multidisciplinary team meeting based on the spider web with domain specific explanation to create a personalised care plan and assign a care coordinator to each patient.
4. Execution of the personalised care plan and frequent pro-active contact between care coordinator and the patient. In the first 12 weeks there is a minimum of 3 contact moments, however more frequent contact is expected. The proactive nature of this contact is emphasized.
5. Follow-up of the personalised care plan using clinical review and at least one multidisciplinary meeting. If needed, ad hoc additional meetings can be organised.

Nature and extent of the burden and risks associated with participation, benefit and group relatedness:

Participation in this study is expected to be low risk for the patients. However, both risks and benefits are associated with participation.

Benefits include: Improved knowledge and insight. Participation might lead patients to have a better understanding of the factors that contribute to their overall well-being. This can be achieved with analysing the six life domains of the positive health conversation tool. This insight might result in appropriate interventions that meet the needs of the hotspotters.

A potential risk that should be taken into account is temporary elevated stress. Hotspotters experience a combination of different problems which can make life more complex and challenging. The heightened emphasis, especially in the beginning, on the factors that contribute to their health and social problems could result in higher stress levels in some participants.

1. INTRODUCTION AND RATIONALES

The term 'hotspotters' was first introduced in Gawande's landmark article (Gawande, 2011). He suggested that the accumulation of problems and high hospital costs were concentrated in certain areas (also defined as 'hot spots') in Camden, New Jersey. When looking at medical care data he noticed that there was a small group of people located in these areas, who accounted for most of the medical costs. It was revealed that one per cent of the hundred thousand people who used Camden's medical facilities, accounted for thirty per cent of its costs (Gawande, 2011).

These so called 'hotspotters' are defined as people who have complex problems on multiple life domains, treated with fragmented care which is difficult to manage by patients and care providers, leading to high medical costs, little effect of the care and persistent unmet needs. Next to their high medical spending levels, hotspotters experiences with the healthcare system are low as the healthcare system is not (yet) successful in dealing with their needs. Furthermore, this group places a lot of strain on healthcare professionals as their problems require a multidisciplinary supply of healthcare services, often in combination with social care and welfare (Wammes et al., 2017; Lee, Whitman, Vakharia, Taksler, & Rothberg, 2017). Various studies claim that the current healthcare system produces a lot of waste of resources in the hotspotters group (Lantz, 2020). Due to the lack of coordination and reactive character of the care, many healthcare providers dealing with these patients are confronted with acute situations that could be prevented.

Currently in The Netherlands, the ad hoc care as usual approach is the standard when treating any patient, including hotspotters. This type of care is concentrated around the general practitioner (GP), home care, mental health and social care. Hotspotters' problems have are multidimensional and addressed by an ad hoc network of care providers. A central caregiver or coordinator is often lacking. All these different care providers respond reactively on symptoms and problems presented by the patient, have their own perspective and treat the patient from their own treatment options. The various care providers are not stimulated to work proactively together.

In a pilot study performed in Portland Oregon showed that in patients with overuse and having a chronic condition, mental problems and substance abuse, the spending was at least 4 times higher than in a person with just a chronic condition. After a relatively simple intervention with health resilience workers the median number of ED visits was reduced from annually 9.3 to 6.2 and of hospital admissions from 2.0 to 1.3 (Bisognano & Kenney, 2012). Based on this experience, a pilot was done in 2017 in two healthcare centres in Zoetermeer.

The pilot study in the Netherlands (Zoetermeer) concentrated on a group identified hotspotters. In the two healthcare centres twenty-five hotspotters with multiple problems were enrolled. These 25 patients received an extensive interview based on positive health methodology, followed by welfare-support according to the individual needs. The one year results of the pilot demonstrated that positive health based on the positive health-tool of Machteld Huber improved in the overall group from a mean score of 5.5 (1.5 sd) to 6.7 (1.1 sd) ($t= 7.33, p<0.01$), which is 22% (Huber et al., 2011). Due to methodological study design issues (observational data with the regression to the mean effect in a group with extreme health care utilisation) the evidence remains promising, but not convincing. The small

number of RCTs performed showed mixed results (Iovan, Lantz, & Shapiro, 2018; Lantz, 2020; Iovan, Lantz, Allan, & Abir, 2020).

This intervention requires a different organization of care for complex patients. The integrated and proactive nature of the proposed approach for patients identified as hotspotters ensues an improved holistic approach. Since evidence for an integrated and proactive approach for hotspotters is not substantial yet, a proper cost-effectiveness study is needed to provide evidence if the approach is worth the effort.

1. OBJECTIVES

The primary goal of this study is to get insight in the cost-effectiveness after 12 months of working with a proactive, integrated (social) care approach in patients fitting our definition of a hotspotter. A hotspotter is a patient with problems on two out of three health domains (chronic somatic, psychiatric and/or social) and at least 2 acute care activities in the previous 12 months. The medical data from 3 years prior to the start of the study will be used to analyse the costs and utilisation of care. This extended period used for data analysis was deliberately chosen to include a timeframe during and before the SARS-CoV-2 pandemic. Since it is yet unknown how the pandemic and its subsequent measures affected our population and their usage of care.

Hypothesis: We hypothesise that after one year of working with a proactive approach of integrated care to improve the care for patients with problems on two out of three health domains (chronic somatic, psychic and/or social) and at least 2 acute care activities in the previous 12 months will result in reduction in volume and spending of acute care, improvement in experienced health and in patient experience.

Research questions:

Is proactive integrated care cost-effective and result in better patients experience than usual care after 12 months for patients with problems on multiple life domains?

Primary outcomes: Incremental cost-effectiveness from a societal perspective. Information on cost will be based on patient-reported data obtained by questionnaires supplied with data from the GP medical files (*Huisarts informatie system, HIS*) and through CBS microdata. To assess the effectiveness the EQ-5D-5L will be used for determining quality of life.

Secondary outcomes:

Insight into patients experience of care:

Insights into the experiences of care will be gathered during a focus group and information about self-efficacy (PAM-13 and SE+IN itemlist), proactive coping (UPCC), and quality of life (SF-12) will be collected using questionnaires (Hibbard, Mahoney, Stockard, & Tusler, 2005; Bode, & de Ridder, 2008; Turner-Bowker, & Hoque, 2014). A questionnaire on experience of care has been considered, but no validated and appropriate questionnaires for this population are available. Therefore, for insight and rich information on the experienced care the format of a focus group was chosen.

Process evaluation:

A process evaluation of this study will be done simultaneously, as a process evaluation can provide valuable insight on the practicalities of the intervention. This information is useful for

future implementation of this intervention. Data on recruitment and reach of the population will be gathered during the inclusion of patients in this study. Integration of care will be collected by using the Integration Meter, patient satisfaction with care using a modified version of the NPS (Reichheld, 2003; Krol et al, 2015), and the nature of the communication between care professional and patient, will be assessed using a HCCQ questionnaire (Jochems, Duivenvoorden, van der Feltz-Cornelis, & van Dam, 2014; Czajkowska, Wang, Hall, Sewitch, & Körner, 2017) and an observation questionnaire (OPTION5) for shared decision making based on audio records. Furthermore, a questionnaire will be used combining the assessment of the acceptability (Acceptability of Intervention Measure - AIM), appropriateness (Intervention Appropriateness Measure - IAM), feasibility (Feasibility of Intervention Measure – FIM), and perceived and experienced effectiveness of the intervention (Weiner, Lewis, & Stanick, 2017) (see F1).

Through focusgroups with the involved care professionals the following themes of process evaluation will be discussed:

- Fidelity (the extend to which the intervention is executed conform protocol)
- Dose delivered (the extend in which the intervention is offered)
- Dose received (the extend in which the patient received the offered care)
- Context (other factors not related to this protocol that might have an influence on the outcomes)
- Satisfaction (the extend to which the care providers are satisfied with the intervention and procedures)

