All clusters start to collect control data at the same time ($t=0$). The 20 clusters will be divided into four groups evenly and each group will be randomly assigned one of four time points at which they will start to implement the proactive integrated care intervention. The first switch will be after 2 months ($t=2$). Every subsequent 2 months a next group of general practices will switch to the intervention mode until all groups have started the intervention. All groups will continue with the intervention as described in this protocol for a total of 12 months. After the 12 months of intervention, care will be delivered as usual. There is no objection if care providers and patients wish to maintain certain aspects of the intervention. All measurements and timepoints after the switch to the intervention falls under the intervention period. The total duration of this study comprises 22 months. This results in varying control period ranging from 2 to 8 months. The total of intervention and follow-up period vary from 14 to 20 months. This time table is summarized in the following chart.

In order to achieve more accurate answers from patients and in turn more reliable results, a member of the research team will administer the SF-12, and questionnaires on proactive coping (UPCC), and self-efficacy (PAM-13 and SE+IN) during a face to face interview, as these might require extra guidance when filling in. This will be done at three time points for each group (before the start of the intervention, at the end of the intervention, and two months after the intervention has ended).

[figure not shown]

Figure 1. This figure depicts the time schedule of this study. The EQ-5D-5L is administered 7 or 8 times, depending on cluster, and is depicted as a square. The Care and Work questionnaire is depicted with an arrow. The questionnaires PAM, SE+IN, SF-12 and UPCC are administered thrice: at the start and end of intervention and two months after ending the intervention (star). The dot represents the HCCQ and adapted NPS at 6 months after the start of the intervention. Focus groups (triangle) are organised per cluster, after finishing the intervention.

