The 'cost and utilization and EQ-5D-L5 questionnaires will be filled in at 7 or 8 different timepoints, which will result in 7 or 8 measurements per participant. Participants are asked if they prefer a questionnaire on paper per post or one per email (using Castor). After receiving the questionnaire participants have one week to fill out the questionnaire. If there is no response, patients are called and offered an interview by phone on the questionnaire. The first interview will be done at the start of the study (t=0). Afterwards information for the questionnaires will be gathered 6 or 7 more times, see figure 1 in §3 study design for an overview and timing of questionnaires. In order to achieve more reliable results, a member of the research team will administer the SF-12 and other secondary study parameter questionnaires that might require extra guidance, during a face to face interview at three time points (before the start of the intervention, at the end of the intervention, and three months after the intervention has ended).

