5.1.2 Secondary study parameters: Patient experience of care

The secondary study parameter is insight into the patient experience of care. To assess their experience focus groups will be organized. A questionnaire on experience of care has been considered, but no appropriate and validated questionnaires for this population are available. Therefore, the format of a focus group was chosen. Focus groups will be organized at 4 different timepoints (t=14, t=16, t=18 and t=20) and each focus group will consist of 6 to 12 patients. For each timepoint several focus groups will be organized. The exact size of the group and number of organized groups, will depend on the number of patients that choose to participate. Four main topics will be discussed, namely: care before the new approach, the new approach, the collaboration between the professionals and the experienced effects of the new approach (see F1).

The presence of proactive coping skills will be quantitatively measured with the *Utrechtse Proactieve Coping Competentie lijst* (UPCC). This is a 21-item questionnaire that measures self-rated proactive coping competences. The questionnaire has been validated in different adult Dutch patient groups. (Bode et al., 2008) (see F1).

Self-efficacy will be measured using two different instruments. The first is the validated Patient activation Measure (PAM-13). This is a 13-item instrument that measures self-reported knowledge, skills and confidence in managing one's health. With this instrument patients can be categorized in four levels of activation (Hibbard et al., 2005). The second questionnaire is the Self-efficacy and Intention itemlist (SE+IN Itemlist). This measures (action and maintenance) self-management self-efficacy, the intention to perform certain self-management behaviors and the presence of certain self-management behaviors. This itemlist was specifically created for this study, as there aren't any questionnaires that are geared towards understanding behavior change in this complex and heterogeneous group of patients. The itemlist consists of 22-items and was created using the Health Action Process

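### The research question promises better patient experience than usual care at 12 months, but no patient-experience or psychological measure has a concurrent usual-care comparison

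*Protocol*

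**What the plan says.** The Objectives section of the protocol poses the research question as "Is proactive integrated care cost-effective and result in better patients experience than usual care after 12 months"; the Summary repeats it as "Is proactive integrated care cost-effective and does it result in better patients experience than usual care after 12 months". The Summary's design paragraph says experience will be assessed both qualitatively and with validated questionnaires. Its list of secondary parameters puts SF-12, UPCC, PAM-13 and the self-efficacy item list under patient experience.

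The timing of each measure is fixed:

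- **Switches (section 3):** at t=2, 4, 6 and 8 months, five practices each, then 12 months of intervention.
- **SF-12, UPCC, PAM-13, SE+IN (sections 3 and 5.3):** three times per group, "before the start of the intervention, at the end of the intervention, and two months after the intervention has ended". Section 5.1.1 differs on the last visit: "at the end of the intervention, and three months after the intervention has ended".
- **HCCQ and adapted NPS (section 5.3):** once, six months into the intervention.
- **Patient focus groups (section 5.1.2):** "Focus groups will be organized at 4 different timepoints (t=14, t=16, t=18 and t=20" months, covering "care before the new approach, the new approach, the collaboration between the professionals and the experienced effects of the new approach". The Objectives give the reason for this format: "for insight and rich information on the experienced care the format of a focus group was chosen".

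Section 6 plans multilevel models with patient, practice and randomised group as levels, continuous study time with practice-specific trends, and continuous time on intervention.

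**The concern.** A stepped wedge supports a randomised comparison because, at the same calendar time, some practices are on usual care and others have switched. That holds for an outcome only if it is measured in both states while both exist. Here the experience and psychological measures are tied to each group's own switch and are skipped in the months when the conditions overlap.

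If the question stands as worded, the report will be expected to say whether experience was better than usual care, and readers will take that as a randomised finding. The data would be close to uncontrolled before-after data. The Introduction judges the pilot on that ground: because of the "regression to the mean effect in a group with extreme health care utilisation) the evidence remains promising, but not convincing". The pilot gain was (6.7 − 5.5)/1.5 = 0.8 baseline SD. Patients in this trial are again selected on at least two acute care encounters in the past year.

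**Working it through.** **1. The plan's timetable reproduces.** With switch time s = 2, 4, 6, 8: the last group ends at 8 + 12 + 2 = 22 months; intervention plus follow-up is 22 − s = 20, 18, 16, 14 months; focus groups at s + 12 = 14, 16, 18, 20. All agree with sections 3 and 5.1.2.

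**2. When each measure is taken, by condition.**

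| Measure | Under usual care | Under intervention or follow-up | Shared months |
|---|---|---|---|
| HCCQ, adapted NPS (s+6) | none | 8, 10, 12, 14 | 0 |
| Patient focus groups (s+12) | none (recalled only) | 14, 16, 18, 20 | 0 |
| SF-12, UPCC, PAM-13, SE+IN (s, s+12, s+14) | 2, 4, 6, 8 | 14, 16, 18, 20, 22 | 0 of 9 |

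The gap for the four questionnaires is 14 − 8 = 6 months, or 8 if the pre-measure is 2 months before the switch. With section 5.1.1's three-month wording the later months are 14, 16, 17, 18, 19, 20, 21 and 23. There are still none shared, and month 23 lies beyond the stated 22-month duration.

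**3. What a linear time trend buys.** Take 20 practices of 10 patients, no dropout, outcome SD 1, random practice and patient intercepts, and a 0/1 intervention indicator. Let κ be the ICC and ρ the within-patient correlation. Section 4.4 uses κ = 0.1, but for spending. I assume κ = 0.05 to 0.1 and ρ = 0.5 to 0.8, with the pre-measure 0 or 2 months before the switch.

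Without a time term the estimate is the mean of two follow-ups minus one pre-measure:

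SE² = 1.5(1 − ρ)/200.

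With a common linear trend, the slope times L is subtracted. L is the distance from the pre-measure to the mean follow-up time: 13 months, or 15 with the earlier pre-measure.

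SE² = 1.5(1 − ρ)/200 + L²/I, where I = 400/(1 − ρ) + 100/[κ + (ρ − κ)/10 + (1 − ρ)/30].

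The 400 is 200 patients × 2, from two follow-ups two months apart. The 100 is 5 × (9 + 1 + 1 + 9), the spread of the switch times around month 5.

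Example, κ = 0.05, ρ = 0.5, L = 13: I = 800 + 100/0.1117 = 1,695.5; SE² = 0.00375 + 169/1,695.5 = 0.1034; SE = 0.32.

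| κ | ρ | L | SE, no time | SE, linear time | Ratio |
|---|---|---|---|---|---|
| 0.05 | 0.5 | 13 | 0.061 | 0.32 | 5.3 |
| 0.05 | 0.8 | 13 | 0.039 | 0.25 | 6.5 |
| 0.10 | 0.5 | 15 | 0.061 | 0.40 | 6.5 |
| 0.10 | 0.8 | 15 | 0.039 | 0.30 | 7.7 |

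The effect detectable with 80% power (2.80 × SE) moves from 0.11–0.17 SD to 0.70–1.12 SD. With the last visit at three months, 900 replaces 400 and L is 13.5 or 15.5; the ratio is then 4.4 to 5.7.

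**4. What the trend does not remove.** A step in the outcome anywhere between months 8 and 14 is 0 for every pre-measure and 1 for every later one. That is the intervention indicator itself, so its coefficient takes up the step in full (1.00), with or without the linear term.

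**The case against.** **The secondary outcome is framed as insight, and the process measures are already descriptive.** HCCQ and NPS sit under process evaluation, section 6 says the implementation analysis is descriptive, and the focus-group format is a reasoned choice. This stands, and it narrows the conflict to the research question in the Summary and Objectives. It does not remove it, because the question is explicitly comparative.

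**The pre-measures are staggered over randomised groups, so they carry some information on the usual-care trend.** True, and more than the pilot reported. But they cover only months 2 to 8, and step 3 shows how little precision remains once the trend is carried to month 14 and beyond.

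**Labelling of secondary analyses belongs in the SAP.** Partly right. The SAP can hold the modelling detail. It cannot supply control observations that the protocol does not collect, and the comparative question is in the protocol.

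**Stronger readings that a reader might infer.** One is that the section 6 model cannot be fitted to these questionnaires because time on intervention is confounded with calendar time. That needs fixed practice intercepts, a pre-measure exactly at the switch, and exposure counted beyond month 12. Section 6 makes practice a random level, section 3 returns care to usual after 12 months, and sections 3 and 5.3 place the pre-measure ahead of the start. Changing any one of these conditions removes the confounding. Another is that the effect is inestimable with calendar-period terms; that is not the planned model. A third is that experience is gathered by focus groups alone; the Summary and section 6 also mention interviews, without giving timing for patients.

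**Conclusion.** The point holds as a mismatch between the stated question and the fixed schedule. There are no usual-care values for HCCQ or NPS, no focus groups under usual care, and no calendar month in which SF-12, UPCC, PAM-13 or SE+IN is measured under both conditions. The comparison with usual care is not impossible to compute for those four questionnaires. It rests on a linear trend carried over at least 6 months, with a standard error about 5 to 8 times larger under the two-month wording and the stated assumptions, and with no protection against a shift inside the gap. Section 6's practice-specific trends would not make that standard error smaller.

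The timing result needs no assumption beyond the stated schedule and does not depend on whether the last visit is at two or three months. Only the size of the standard error depends on the assumed correlations.

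The point concerns a secondary aim. A reader might infer either that the primary outcome is undermined or that it is unaffected; neither was assessed here. EQ-5D-5L and the cost questionnaire follow a different, repeated schedule from t=0.

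**What to change.** - **Summary and Objectives:** drop the comparison with usual care at 12 months from the patient-experience part of the research question. Ask instead how SF-12, proactive coping and self-efficacy change from before to after the intervention, and how patients describe their care under it.
- **Sections 5.1.1 (SF-12), 5.1.2 and 6:** state that the four questionnaires support a before-after conclusion without concurrent control, open to time trends and regression to the mean; that any trend-adjusted estimate relies on linear extrapolation over at least 6 months; and that HCCQ, NPS and the qualitative data are descriptive.
- **Section 5.1.1 against sections 3 and 5.3:** reconcile the two-month and three-month wording for the last visit.

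This is one wording amendment, with no added measurement, visit or patient burden. The price is a weaker claim for a secondary aim.
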